9. STATISTICAL CONSIDERATIONS

Statistical analysis will be done by the sponsor or under the authority of the sponsor. A general description of the statistical methods to be used to analyze the effectiveness and safety data is outlined below. Specific details will be provided in the SAP.

The primary study objective will be addressed by comparing the mean change in KCCQ TSS from baseline to Month 3 between the study intervention groups. The key secondary study objective will involve a comparison between the 2 randomized groups in terms of the mean difference in daily step counts from baseline to Month 3. For analyzing the primary, secondary, and exploratory objectives, an intent-to-treat (ITT) population comprising of all randomized participants will be used. Specific imputation rules for missing data (eg, missing KCCQ TSS, daily step count) will be applied, if warranted, and will be specified in the SAP before the final database lock. Descriptive statistics such as mean, median, standard deviation, interquartile range, minimum and maximum will be used to summarize continuous variables. Counts and proportions will be used to summarize categorical variables. Graphical data displays (eg, box plots) may be employed to summarize data. For time to event variables, Kaplan-Meier estimates over time will be plotted. All statistical tests will be two-sided and performed at the 5% significance level unless otherwise specified. No multiplicity adjustment to the overall Type I error rate will be applied when analyzing the exploratory variables.

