9.4. Statistical Analyses

9.4.1. Handling of Missing Data

Missing data affecting the primary endpoint change in KCCQ TSS will be addressed via the MMRM method that assumes missingness at random (MAR). Specific imputation rules including statistical modeling approaches may be employed when such an assumption is not valid. In cases where individual items in the KCCQ domains are missing or not completed at required times, appropriate rules to impute missing item scores will be specified based on the KCCQ manual. Sensitivity analyses will be conducted to assess impact of missing data on key study results. Further details about the imputation rules and sensitivity analyses will be provided in the SAP.

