5.1.2. Data Handling Rules

This study will obtain mainly 3 types of data for statistical analysis: the smartphone/app-based PRO data, the activity data collected from the Fitbit device and the claims data on adverse events (including clinical outcomes, prescription fills, and related HRU). In addition, participant's self-reported AE data collected via a Call Center will be directly sent over to Janssen Safety separately and is described below as well. All data will be received and processed by PRA (3rd party vendor, see [Appendix 5: CHIEF-HF Study Data Flow Diagram](#)) into analysis files based on specifications provided by the sponsor/study SAP unless specified otherwise.

Smartphone Data - PRO Measures

PRO data (ie, KCCQ, PGIC and PGI-S, participant satisfaction survey) will be collected via the smartphone apps available with participants. Based on the administration of the KCCQ at screening/baseline through an app, an overall summary score will be produced to decide eligibility of individual participant into the study. The individual domains and summary scores of KCCQ will be calculated using the scoring algorithm provided in the KCCQ manual at specified time points during the study. Missingness in these PRO measures may result from participants not completing the questionnaires on the smartphone app at the scheduled times during the study period for various reasons including non-compliance with the protocol, discontinuation due to AE, loss to follow up, etc.

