Missing and incomplete data in KCCQ PRO measure may be of 2 types: missing at the form-level and at the item-level. Form-level missing data refers to a participant missing an entire PRO assessment for a scheduled time point. If not otherwise specified, analyses will be conducted on all available data and form-level missing data will not be imputed. For the KCCQ, derivation of individual domain scores in the presence of missing item-level responses will follow algorithms specified in the KCCQ manual. PRA will calculate baseline KCCQ overall summary score based on the KCCQ app and include in the analysis database. For calculation of all other KCCQ domain scores (including the KCCQ-TSS) at baseline and at all post-randomization time points, scoring instructions available per the KCCQ manual with Janssen will be followed (see Appendix 8). For the PGIC and PGI-S measures, a single imputation (ie, last observed scores carried forward) for missing post-baseline scores will be used as a conservative rule. Vertical file formats will be prepared for all PRO data, reading one record per patient for each measurement time (ie, baseline, Weeks 2, 4, 6, and 12, and Months 6 and 9, respectively).

Fitbit Data - Clinical (Activity) Measures

Data from the Fitbit device pertaining to the daily total step counts and daily total floors climbed will be aggregated over 2-week intervals for the entire study duration (see [Table 1](#)). Due to the general sedentary nature of HF patients, Fitbit recorded <100 steps taken in a day will not be

considered in the calculation of averages for daily step counts . If missing >7 days (50%) in a 2-week interval, the corresponding 2-week interval average will be set to missing.

In case of premature discontinuation of the study intervention, the average of the last non-missing 14-day window prior to the last dose of study intervention will always be used as an EOT value. If the EOT value corresponding to the period (EOT-14, EOT-1) is missing (not valid), the EOT period will be rolled back by one day, ie, (EOT-15, EOT-2), (EOT-16, EOT-3), until a non-missing (valid) value is available. This corresponds to a last observation carried forward (LOCF) up to Week 12/EOT approach. If no post-baseline daily activity data have been collected for at least 7 days over a 14-day time window, no EOT value will be computed, and the post-baseline value will be set to missing.

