An MMRM model assumes the KCCQ-TSS data missing at random (MAR). A sensitivity analysis may be performed involving multiple imputation (MI) modeling approach for missing KCCQ-TSS values when the MAR assumption is considered not valid. Implementing the MI process requires 3 steps: 1) each missing value is imputed multiple times, based on statistical modeling, resulting in repetitions of the original dataset, along with the newly imputed values (implemented in the Statistical Analysis System [SAS] using PROC MI); 2) each dataset is analyzed using an MMRM model (implemented in SAS using PROC MIXED). The LS means and SEs from each analysis will be output to a SAS dataset; 3) results from the analyses performed on multiple datasets in step #2 are combined to provide valid statistical inference (implemented in SAS using PROC MIANALYZE).¹

A complete SAS code for MMRM model and implementation of the MI approach described above will be added to the final SAP appendix or to the final study report. Mortality in this short-duration trial is expected to be low and to be comparable between groups and will be ignored in the primary analyses of mean differences in changes in KCCQ total symptom scores, but can be included in the responder analyses (described below) by assigning them to the lowest response (greatest deterioration) category. Should there be a >5% mortality rate in this study, and if it is unequally distributed between treatment arms, then joint modeling of survival and health status (e, g., KCCQ) will be performed. A win-ratio approach^{19,20} may also be considered by analyzing the KCCQ-TSS score as a composite, rank-based outcome, incorporating participant vital status at 12 weeks along with a change in score from baseline to 12 weeks in surviving participants. This essentially is the rank analysis of covariance method, with a corresponding win ratio used to estimate the magnitude of treatment effect.

An exploratory responder analysis will be performed when comparing proportions of participants with a 5- (or 10-) point improvement in the KCCQ-TSS from baseline to Week 12 between the groups. This will be based on a 2-sample difference in proportions test along with a 95% confidence interval for the difference in 2 proportions.

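### The missing-data sensitivity analysis that the protocol commits to for KCCQ-TSS is optional in the SAP, has no testable trigger, and specifies neither an imputation model nor a departure from MAR

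*SAP*

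**What the plan says.** **Protocol.** Section 9.4.1 handles missing KCCQ-TSS by an MMRM under MAR and allows other modelling approaches if MAR does not hold. It then states without condition: "Sensitivity analyses will be conducted to assess impact of missing data on key study results". It adds: "Further details about the imputation rules and sensitivity analyses will be provided in the SAP". The opening of Section 9 says that specific imputation rules "will be applied, if warranted, and will be specified in the SAP before the final database lock".

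**SAP.** Section 5.2.3 confirms that the primary MMRM assumes MAR. Its only general missing-data sensitivity analysis of KCCQ-TSS is this: "A sensitivity analysis may be performed involving multiple imputation (MI) modeling approach for missing KCCQ-TSS values when the MAR assumption is considered not valid". Three steps follow: PROC MI, an MMRM in PROC MIXED on each completed dataset, and PROC MIANALYZE to combine them. On the code, the SAP says that "implementation of the MI approach described above will be added to the final SAP appendix or to the final study report". Section 5.1.2 sets the default for whole missing questionnaires: "If not otherwise specified, analyses will be conducted on all available data and form-level missing data will not be imputed".

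Section 5.2.3 also has provisions for deaths. The only firm one is conditional: "Should there be a >5% mortality rate in this study, and if it is unequally distributed between treatment arms, then joint modeling of survival". That model would take in the KCCQ as well. The win ratio and the lowest-category assignment in the responder analysis are optional.

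**The concern.** The protocol makes a commitment and hands the detail to the SAP, and the SAP returns a permission. MAR cannot be confirmed or refuted from observed data, so a trigger that depends on MAR being judged invalid has no objective way to fire. If it did fire, the steps listed name no mechanism that departs from MAR.

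Missing values are expected and could be informative. The KCCQ is completed on a smartphone app, and SAP 5.1.2 expects missed questionnaires for reasons "including non-compliance with the protocol, discontinuation due to AE, loss to follow up". SAP 5.2.2 treats loss to follow-up, withdrawal and death as missing data. If participants who stop answering do worse than the model predicts from their earlier scores, and this differs by arm, the Week 12 difference is biased. Nothing that is certain to be run would show how large the departure must be to change the conclusion.

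**Working it through.** **1. Commitment against delivery.**

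| Question | Protocol 9 and 9.4.1 | SAP 5.2.3 |
|---|---|---|
| Will it be run? | Yes, unconditionally | Optional |
| Trigger | None | A judgement that MAR is invalid; no criterion |
| Imputation model, number of imputations, seed | To be in the SAP | Not given |
| Departure from MAR (delta, reference-based rule, tipping point) | Not promised | Not given |

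**2. Does anything else fill the gap?**

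- Joint modelling needs mortality above 5% and unequal between arms, and it concerns deaths only.
- The win ratio and lowest-category assignment are optional and also concern deaths.
- The per-protocol repeat (SAP 2.3.3) changes the population, not the missing-data assumption.
- The carry-forward rules in SAP 5.1.2 apply to PGIC, PGI-S and activity data, not to KCCQ-TSS.

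**3. The plan's own figures** (normal approximation, two-sided 5%, SD 18) reproduce. Power is Φ(d / (18 × √(2/n)) − 1.96), with n per arm:

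- n = 950, d = 3: 95.3% (plan: about 95%).
- n = 855, d = 3: 93.1% (plan: above 90%).
- 445 in total, d = 4.8: 80.3% (plan: 80%).
- 400 in total, d = 3.5: 49.4% (plan: 50%).

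The concern disputes none of these.

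**4. How much could a departure matter?** From the documents: SD 18, two-sided 5%, enrolment of 400 to 480, dropout of 5% to 10%, and the 4.8-point effect in SAP 1.4. Assumptions not in the documents: N = 440 as the midpoint, 10% missing in each arm, the size of the shifts, and the observed differences 4.0 and 3.6.

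The SE lies between two bounds:

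- complete data: 18 × √(4/440) = 1.716, so the smallest significant difference is 1.96 × 1.716 = 3.36;
- completers only: 18 × √(4/396) = 1.809, giving 1.96 × 1.809 = 3.55.

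If only missing canagliflozin values are shifted down by delta, the estimate falls by 0.10 × delta. The tipping delta is therefore (observed difference − limit) / 0.10:

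| Observed difference | Limit 3.55 | Limit 3.36 |
|---|---|---|
| 4.8 | 12.5 | 14.4 |
| 4.0 | 4.5 | 6.4 |
| 3.6 | 0.5 | 2.4 |

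Using t instead of normal quantiles lowers each entry by about 0.1. Delta-adjusted MI on simulated data (assumed visit SDs 15 to 18, correlations 0.55 to 0.70, 3% intermittent gaps) gave a mean SE of 1.77 and median tipping deltas of 13.0, 5.5 and 1.5.

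**5. Bias of the MAR estimate.** This is a different scenario: the same shift in both arms, with missing rates that may differ. Bias is about shift × difference in missing rates.

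- Equal rates: about 0.
- 10% v 5%, shift 5: 5 × 0.05 = 0.25 point, or 0.25 / 1.77 = 0.14 SE.
- 10% v 5%, shift 10: 10 × 0.05 = 0.50 point, or 0.28 SE.

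**The case against.** Three stronger readings are tempting, and the documents do not support them.

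- *The protocol promised an analysis under missing-not-at-random.* It did not. Section 9.4.1 promises sensitivity analyses for missing data, and its own sentence about an invalid MAR assumption is permissive, as the SAP's is. The mismatch is between a firm commitment and an option. Requiring a departure from MAR is a standard of good practice added here, on the ground that an analysis sharing the primary assumption cannot show what happens when that assumption fails.
- *The MI described would necessarily assume MAR.* That is an inference. PROC MI can impute under other mechanisms, and the SAP reserves the MI for a failure of MAR. What is certain is that the model is unspecified.
- *The model will be chosen after unblinding.* Protocol 9 requires any imputation rules to be in the SAP before final database lock, and the SAP is to be finalized before lock. Leaving code for the study report is allowed by the SAP's own wording, so its absence is no breach. It remains true that the SAP version dated 1 July 2021 contains no imputation rules for whole missing KCCQ forms.

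Two further points carry weight. The MMRM needs no form-level imputation, so the default in SAP 5.1.2 is not a fault. Losses are also reduced: KCCQ collection continues after study drug is stopped, and the app sends reminders. These measures do not recover participants who leave the study or stop answering.

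On size, the fragile case of 3.6 was chosen because it lies just above the limit. With an SE of 1.773 and 10% missing, the chance of a significant result that tips at 2 points or less is about 4%, and at 5 points or less about 9% to 11%, for true effects between 3 and 4.8. That holds the weight of the concern down but does not remove it.

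**Conclusion.** The concern holds as a gap in specification. The SAP makes optional, and does not define, the missing-data sensitivity analysis that Protocol 9.4.1 commits to, and its trigger cannot be verified from the data.

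Materiality is low to moderate. Under the assumptions in the working (N = 440, SD 18, 10% missing per arm), a 4.8-point result is robust, tipping only at about 12 to 14 points. Results close to the limit of about 3.4 to 3.6 points are fragile. Bias is about zero if missing rates and shifts are equal across arms, and about 0.25 to 0.5 point for an assumed 10% v 5% missing with a 5- to 10-point shift. The arm-specific missing rates and the shifts are not in the documents. This is an improvement the sponsor should make, not a defect that invalidates the primary analysis.

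**What to change.** SAP Section 3 reports the 12-week data before the 9-month data, so the change belongs before the 12-week database lock and unblinding. Replace the conditional sentence in SAP 5.2.3 with one sensitivity analysis that is always run and departs from MAR for missing Week 12 KCCQ-TSS values.

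- An example is a delta-adjusted tipping-point MI that shifts only missing canagliflozin values and keeps every value observed after discontinuation, as the treatment-policy estimand requires. A reference-based MI would also serve.
- State in the SAP the imputation model (for example treatment, stratum, baseline, and Weeks 2, 4 and 6 KCCQ-TSS), the number of imputations, the seed and the delta grid. The grid should be fine enough to resolve tipping points of 1 to 2 points.
- Report the smallest delta that removes significance. If the primary result is not significant, report the estimate and interval over the grid.
- Tabulate missing Week 12 values by arm and reason.
- State that the analysis covers the full analysis set, so randomized participants with no post-baseline KCCQ stay outside it unless it is repeated in all randomized participants.

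The cost is one paragraph and a little programming. The delta range is a judgement, and the reported robustness may look less favourable. The primary MMRM, the estimand and the sample size do not change.

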9.4.2. Effectiveness Analyses

9.4.2.1. Primary and Secondary Effectiveness Analyses

The primary and key secondary effectiveness analyses will be based on the ITT analysis population (using all randomized participants).

As KCCQ TSS is measured repeatedly over time (ie, at baseline, Week 2, Week 4, Week 6, and Week 12 respectively), the primary effectiveness endpoint (change in KCCQ TSS from baseline to Month 3) will be analyzed by a mixed effect model repeated measures (MMRM) method simultaneously adjusting for study intervention group, stratification factor (HF_rEF versus HF_pEF), time, time by study intervention group, and baseline KCCQ TSS value as covariates. An unstructured covariance structure will be assumed across study intervention groups to model the within-participant errors. The primary comparison will be based on the difference in least squares between treatments at Month 3. The treatment difference in the least squares means and their 2-sided 95% confidence interval (CI) will be provided. An MMRM model accounts for data missing at random.

A responder analysis will also be performed when comparing proportions of participants with a 5- (or 10-) point improvement in KCCQ TSS from baseline between the study intervention groups. This will be based on a two-sample difference in proportions test along with a 95% confidence interval for the difference in 2 proportions. Additionally, empirical cumulative distribution functions of the KCCQ TSS and other domain scores will be presented.

The primary effectiveness endpoint will also be analyzed by subgroups defined by age, gender, race and key baseline disease/demographic characteristics using the MMRM approach described above. Further details will be provided in the SAP. Quantitative and/or qualitative interactions for each subgroup and treatment will be identified. Qualitative interactions will be investigated further by the Gail and Simon test⁹ and interpreted accordingly.

The first key secondary endpoint of daily step count will be tested once the primary endpoint is shown to be significant at the 5% significance level using a two-sided t-test. This approach will control for the overall Type I error rate at 5%.

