optional participant satisfaction survey at end of study (via smartphone), step count and floors climbed (via the Fitbit device), medical and pharmacy claims data (including up to 36 months history for eligibility confirmation), HRU and health economics (including hospitalization/readmission due to HF or other reason, ED visits, the duration of stay at each hospitalization/readmission), review of claims for prohibited medications and new diagnoses that may require discontinuation, and adverse events. In addition, information related to outpatient IV diuretics, inotropes and vasodilators and in-patient IV therapies as well will be considered relevant. Note that claims data that involves up to 36 months history to confirm eligibility into this study will not be part of the study database for analysis.

Participants will be of any gender, 18 years of age or older, and will have clinically stable, symptomatic HF with or without type 2 diabetes mellitus (T2DM) with a KCCQ overall summary score <80 prior to randomization, which represents New York Heart Association (NYHA) II and III participants.

Figure 1: Schematic Overview of the Study

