1.5. Randomization and Blinding

Central randomization will be implemented in this study. Participants will be randomly assigned to 1 of 2 study intervention groups based on a computer-generated randomization schedule prepared before the study by or under the supervision of the sponsor before initiation of the study.

Randomization will be balanced by using randomly permuted blocks and will be stratified by EF (HFREF or HFpEF) at study entry as recorded in the participant's electronic health record (EHR).

The interactive web response system (IxR) will generate a randomization code, participant randomization number, and kit number once consent is completed and the participant is confirmed eligible by the virtual principal investigator. The kit number will dictate the study intervention assignment and the matching study intervention bottle(s) to be shipped to the participant directly from the drug distribution vendor.

[figure not shown]
The IxR will provide the kit number of the study intervention bottle(s) to be dispensed for each randomly assigned participant of the double-blind treatment period. Based on these randomization codes, study intervention will be packaged and labeled in a manner that maintains the double-blinded nature of the study.

The drug depot will not be provided with randomization codes. The codes will be maintained within the IxR, which has the functionality to allow the virtual principal investigator or designee to break the blind for an individual participant.

Under normal circumstances, the blind should not be broken until participants have completed the 12-week, double-blind treatment period. The virtual principal investigator or designee may in an emergency determine the identity of the study intervention by contacting the IxR. In the event the blind is broken, the sponsor must be informed as soon as possible. The date and reason for the unblinding must be documented in the study database. All randomization codes will be released after completion of the study. Participants who have had their intervention assignment unblinded should continue to perform their scheduled evaluations.

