5.2.3. Analysis Methods

The primary effectiveness endpoint analysis will be based on the full analysis set (FAS).

Considering the repeated measurements of the KCCQ-TSS in the double-blind treatment period (ie, at baseline, Weeks 2, 4, 6, and 12 respectively), the primary effectiveness endpoint (change in the KCCQ-TSS from baseline to Week 12) will be analyzed by a MMRM method simultaneously adjusting for treatment, stratification factor (HF_rEF or HF_pEF), time, time by treatment, and baseline KCCQ-TSS value as covariates. Time is repeated within participants and an unstructured covariance structure will be assumed across treatment groups to model the within-participant errors. Fixed effects tests will be computed using the Kenward-Roger method to determine the degrees of freedom of the denominator. In case of convergence issues, alternative variance-covariance structures will be evaluated in the following order, with the first structure in the following list that converges being used in the analysis: heterogeneous Toeplitz, standard Toeplitz, and AR (1) with separate participant random effect. The primary comparison will be based on the difference in the LS mean changes from baseline to Week 12 between treatments. The treatment difference in the LS means, corresponding 95% confidence intervals (CI) and associated p-value will be calculated. The LS means \pm SE of change from baseline values estimated by MMRM will be plotted by each timepoint for each intervention group.

```
PROC MIXED DATA=analysis_dataset;
CLASS treatment time ptid;
MODEL change = treatment time treatment*time baseline strat_var/DDFM=KR;
REPEATED time / SUBJECT=ptid TYPE=UN;
LSMEANS treatment;
LSMEANS treatment*time/pdiff cl;
RUN;
```

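### The exploratory KCCQ-TSS responder comparison is valid but gives up precision by not adjusting for baseline TSS, which the primary model already uses

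*SAP*

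**What the plan says.** SAP 5.2.3 gives the status and the endpoint: "An exploratory responder analysis will be performed when comparing proportions of participants with a 5- (or 10-) point improvement in the KCCQ-TSS", measured from baseline to Week 12. The method follows: "This will be based on a 2-sample difference in proportions test along with a 95% confidence interval". Protocol 9.4.2.1 has the same test ("This will be based on a two-sample difference in proportions test along with a 95% confidence interval for the difference in 2 proportions"), and so does the protocol synopsis. Neither document adds a stratified or covariate-adjusted version.

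The primary MMRM in the same SAP section is specified as "adjusting for treatment, stratification factor (HF_rEF or HF_pEF), time, time by treatment, and baseline KCCQ-TSS value as covariates". SAP 1.5 states that randomization "will be stratified by EF (HFREF or HFpEF) at study entry as recorded in the participant's electronic health record (EHR"). Both covariates are therefore in the analysis data.

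Entry is restricted on the overall summary score, not on the TSS. SAP 1.2 requires a "KCCQ overall summary score <80 prior to randomization"; protocol 5.1 sets the limit at 80 or below. The difference between the two limits does not affect this point.

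**The concern.** The responder comparison uses the same score at the same visit as the primary model but drops that model's two baseline covariates. Other analyses in the SAP keep them. The step-count t-test is paired with an adjusted MMRM (5.3.3), the exploratory Cox models include the stratum (5.4.2), and the hospitalization log-rank test is stratified by EF type (section 9).

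Two things are at stake. First, baseline TSS is likely to predict whether a participant gains 5 or 10 points, so leaving it out widens the interval. Second, a chance difference in baseline TSS between arms passes directly into the unadjusted risk difference.

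The result is not decisive, but it will be read. SAP 1.4 interprets a 3- to 5-point mean difference as more participants having clinically important improvement, and 5.2.3 has responder analyses supplement the mean difference. With expected enrollment down from 1,900 to about 400-480 (SAP 1.4), the interval is already wide.

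**Working it through.** **The plan's own figures.** The documents give no power or expected rates for the responder comparison, so only the primary-endpoint figures can be reproduced. With a two-sided 5% level and SD 18, power = Φ(δ / (18·√(4/N)) − 1.96).

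- N = 1,900, δ = 3: standard error 18·√(4/1,900) = 0.826; 3/0.826 − 1.96 = 1.67; power 95.3% (stated about 95%).
- N = 445, δ = 4.8: standard error 1.707; 4.8/1.707 − 1.96 = 0.85; power 80.3% (stated at least 80%).

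Both reproduce.

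**Can participants at the ceiling enter?** The overall summary is the mean of four scores (SAP Appendix 8). With TSS = 100 and an overall summary of 80, the other three scores need a mean of (4 × 80 − 100)/3 = 73.3. With TSS = 95 the figure is (320 − 95)/3 = 75. So baseline TSS above 95 (no room to gain 5) or above 90 (no room to gain 10) is compatible with entry. The documents do not say how often this will occur.

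**Precision, by simulation.**

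- Inputs from the documents: change SD 18, 1:1 allocation within EF strata, scores limited to 0-100, thresholds 5 and 10, difference 4.8 points, and N = 440 as the middle of 400-480.
- Assumptions: baseline TSS mean 60 or 70, SD 20; baseline-change correlation r from -0.10 to -0.45; placebo mean change 4; strata 50:50 and 2 points apart in mean change; no missing data. The overall-summary limit was not modelled.
- Comparison: the unadjusted difference in proportions against a logistic model with treatment, stratum and baseline TSS, standardized to a marginal risk difference.
- Efficiency = (unadjusted SE / adjusted SE)², from unrounded SEs. CI half-width = 1.96 × SE.

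Results for the 5-point responder (about 48-49% on placebo, 57-60% on canagliflozin):

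| Baseline mean, r | SE unadjusted → adjusted | Efficiency | CI half-width (percentage points) | Power |
|---|---|---|---|---|
| 60, -0.10 | 0.0472 → 0.0467 | 1.02 | 9.3 → 9.2 | 58% → 58% |
| 60, -0.30 | 0.0472 → 0.0453 | 1.08 | 9.3 → 8.9 | 56% → 59% |
| 60, -0.45 | 0.0471 → 0.0436 | 1.17 | 9.2 → 8.5 | 58% → 66% |
| 70, -0.45 | 0.0473 → 0.0427 | 1.23 | 9.3 → 8.4 | 54% → 62% |

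The 10-point threshold gives efficiencies of 1.03 to 1.23. Repeat simulations over the same range of assumptions ran from about 1.01 to about 1.3. Adjusting for the stratum alone changes the SE by at most about 0.0002, so nearly all the gain comes from baseline TSS. In these settings the mean risk difference is the same under both methods to within 0.001. With no true effect, both tests reject about 4-6% of the time.

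**Chance imbalance.** Before truncation at 0 and 100, the SD of the between-arm difference in mean baseline TSS is 20·√(4/440) = 1.9 points; two SDs are about 3.7 points after truncation. An imbalance of that size moves the unadjusted risk difference by about 1.0 to 4.4 percentage points, against the arm with the higher baseline. The expected difference is about 10 points. After adjustment the shift is under 0.5.

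**Ceiling share.** Under the assumed baselines, about 4-11% have TSS above 95 and 7-16% above 90. These figures only illustrate the assumptions.

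**The case against.** The strongest reply is that nothing here is an error. The analysis is labelled exploratory and lies outside the fixed sequence of SAP 1.3, so no formal conclusion depends on it. The unadjusted difference in proportions is a valid estimator under randomization, and its interval already allows for chance imbalance. The primary MMRM adjusts for baseline TSS, and the cumulative distribution plots show the whole change distribution. The gain depends on a baseline distribution and correlation that the documents do not give; at r = -0.10 it is negligible. All of this stands, and it limits the priority. It does not remove the case for using a covariate that costs nothing to include.

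A reader might infer more than the documents support:

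- *That omitting the stratum is a serious fault.* Under the assumed 2-point shift, the stratum adds almost nothing.
- *That ceiling participants bias the comparison, or that adjustment repairs this.* They are balanced between arms in expectation and dilute the difference. They cannot respond under either method.
- *That only observed Week 12 scores are used.* The responder text does not say so. SAP 5.1.2 leaves missing questionnaires unimputed by default, but SAP 2.1 defines the analysis endpoint as the last recorded post-baseline value. The rule is ambiguous.
- *That deaths are ignored.* SAP 5.2.3 already permits placing them in the lowest response category.
- *That multiple imputation should be required here.* In the SAP it is an optional sensitivity analysis, so the imputed data may never exist.

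**Conclusion.** The point holds as a matter of efficiency in an exploratory analysis, with low to moderate priority. At about 440 participants, adjustment is worth roughly 1% to 30% more participants for the responder risk difference. In the tabulated settings it narrows the CI half-width by about 0.1 to 0.9 percentage points and adds 0 to 8 points of power. Where the gain falls depends on the assumed baseline TSS mean (60-70, SD 20) and baseline-change correlation (-0.10 to -0.45), and it comes almost entirely from baseline TSS. Adjustment also removes most of the effect of a chance baseline imbalance. It leaves the ceiling dilution in place, so that needs to be shown rather than modelled away. The documents do not support calling the planned test biased or invalid.

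**What to change.** In SAP 5.2.3, estimate the 5- and 10-point responder risk differences from a logistic model with treatment, EF stratum and baseline TSS, standardized to a marginal risk difference with a 95% CI. Keep the raw proportions by arm as description. Report by arm how many participants have baseline TSS above 95 and above 90, so that readers can see how many could not meet each threshold.

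The cost is a short SAP edit and a few lines of code. No new data are needed, and the primary analysis, the testing sequence and the optional status of multiple imputation do not change.
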